#### **3.4.2 FARAPULSE Epicardial Ablation Clinical Studies**

**FARAPULSE FIM Epicardial Clinical Study**

In addition, FARAPULSE has shown the preliminary safety and feasibility of Pulsed Electrical Field ablation in an earlier clinical study using the FARAPULSE Cardiac Ablation System for epicardial ablation between September 2016 and March 2017. The data collected in this first study using the epicardial system has supported and informed the design of the FARAPULSE Endocardial Ablation System. Below is a summary of FARAPULSE’s First-in-Man (FIM) clinical study entitled, “First in Human- Phase 1 / 1A safety study of the FARAPULSE, Inc. Cardiac Ablation System used for cardiac tissue ablation for the treatment of atrial fibrillation through open heart surgical procedure.”

This first study was initiated at the Italian Hospital, Asuncion Paraguay in September 2016. Seven (7) patients were enrolled in the study, each patient had been diagnosed with paroxysmal, persistent and/or continuous atrial fibrillation and was scheduled for a cardiac surgery procedure. The purpose of this FIM study was to investigate the safety and acute technical feasibility of the FARAPULSE Cardiac Ablation System to perform epicardial cardiac ablation in treating patients with atrial fibrillation (AF).

Following Ethics Committee approval, patient consent and enrollment in the study, clinical evaluations were conducted and data collected at the following intervals: pre-procedure (baseline), post-procedure, hospital discharge, and 30 day, 3-months (optional), and 6-months post-procedure. The FARAPULSE procedural clinical data were collected and recorded on standardized case report forms at the clinical study site.

There were no device or ablation procedure-related adverse events reported within 7-days post-procedure or at time of discharge. Also, there were no device malfunctions. Additionally, electrical isolation of the pulmonary veins and the posterior left atrium using the FARAPULSE Cardiac Ablation System was achieved in three of seven (3/7) patients. These findings demonstrate the safety and feasibility of applying pulse electrical field energy to the heart to ablate electrically

active myocardium and isolate the pulmonary veins. The same application of energy has been used for endocardial ablation in atrial fibrillation in the IMPULSE study.

#### FARAPULSE IMPACT Clinical Study

In addition, FARAPULSE, Inc. is conducting a safety and feasibility study of the FARAPULSE Cardiac Ablation System at Na Homolce Hospital in Prague, Czech Republic and CHU Bordeaux in Pessac, France under the “IMPACT” Protocol, CS0172. Seven (7) patients have been enrolled between December 2017 and March 2018, four (4) in Prague and three (3) in Bordeaux. All patients were discharged in good condition. One femoral hematoma was noted, which was not investigational device related. The event was resolved. One hospitalization for atrial tachycardia was noted eight months post procedure. The event was resolved.

At the conclusion of the index procedure the posterior left atrium and PVs were isolated in six (6) of seven (7) patients. Six (6) patients have reached the 3-month follow-up assessment. The posterior left atrium and PVs were electrically isolated in one of these patients. In two of the remaining patients there was a small electrical gap, which was closed at the 3-month follow-up using a commercial radiofrequency catheter. In one of these patients, the gap had been present at the conclusion of the index procedure; in the other patient the gap had developed during the follow-up period. Three (3) patients undergoing remapping required multiple radiofrequency lesions at the three-month follow-up. Patients in this protocol will undergo follow-up at 30 days, 3 months, 6 months, and 12 months.

### 3.5 Complications of Catheter Based and Surgical Ablation

The risks and complications associated with thermal or non-thermal cardiac ablation depend on the complexity of the procedure. The most common complications due to cardiac ablations include bleeding, cardiac tamponade, stroke/TIA, pulmonary vein stenosis, phrenic nerve injury, thromboembolism, air embolism, post-procedural arrhythmias, and vascular complications. Further, recurrences of atrial fibrillation (AF) or atrial tachycardia after an initial AF catheter ablation procedure (20 – 40% of patients) are common.

Gelsomino 2014 noted in a study of SAEs (Serious Adverse Event) rates for studies of convergent AF ablation (N=335) (**Table 1**). There were 3 early deaths (0.9%) and three conversions to sternotomy and cardiopulmonary bypass (0.9%). There were no late deaths or thromboembolic events. These SAE rates include both catheter ablation and surgical ablation procedures in the reviewed studies. Expected adverse event rates from an isolated surgical procedure are likely to be lower.

**Table 1: Data from Gelsomino 2014 – Adverse Event Rates for Surgical Ablation**

Event	Frequency (%)
Bleeding	6 (1.8%)
Tamponade	4 (1.2%)
Pleural effusion	1 (0.3%)
Hemothorax	1 (0.3%)
Pneumothorax	1 (0.3%)
Pneumonia	1 (0.3%)

In conclusion, potential risks related to the FARAPULSE Endocardial Ablation System are expected to be no different from those products that are approved and available on the market for catheter-based or surgical ablation procedures.

FARAPULSE testing of the Endocardial Ablation System will ensure the safe use of the device during clinical investigation as well as compliance with the applicable parts of the Medical Device Directive 93/42/EEC. FARAPULSE will also ensure, through its Risk Management System, that the residual risks have been reduced as low as possible. The prior clinical experience using the FARAPULSE Endocardial Ablation System as well as a review of the complications associated with catheter-based cardiac ablation procedures support the execution of this study to further assess the safety and feasibility of the FARAPULSE Endocardial Ablation System.

## **4. Investigational Device**

### **4.1 Name of Investigational Device**

FARAPULSE Endocardial Ablation System

### **4.2 Intended Use**

The FARAPULSE Endocardial Ablation System is indicated for cardiac tissue ablation for the treatment of paroxysmal atrial fibrillation.

### **4.3 Classification**

The FARAPULSE Endocardial Ablation System is comprised of the FARAWAVE Endocardial Ablation Catheter System, the FARASTAR Endocardial Generator System, and the FARADRIVE Deflectable Sheath System.

The FARAWAVE Endocardial Ablation Catheter System is classified as a Class III medical device. Per MDD 93/42/EEC Annex IX Rule 6 applies to the ablation catheter, which defines it as a surgically invasive device intended for transient use (<60 min) that specifically controls, diagnoses, monitors or corrects a defect of the heart or of the central circulatory system through direct contact with these parts of the body.

The FARASTAR Endocardial Generator System is classified as a Class IIb medical device. Per MDD 93/42/EEC Annex IX Rule 9 applies to the generator system,

which defines it as an active therapeutic device that is intended to administer or exchange energy to and from the human body in a potentially hazardous way, taking account of the nature, the density and the site of application of the energy.

The FARADRIVE Deflectable Sheath System is classified as a Class III medical device. Per MDD 93/42/EEC Annex IX Rule 6 applies to the Deflectable Sheath System, which defines it as a surgically invasive device intended for transient use (<60 min) that specifically controls, diagnoses, monitors or corrects a defect of the heart or of the central circulatory system through direct contact with these parts of the body.

[figure not shown]
#### 4.4 System Components: FARAPULSE Endocardial Ablation System

The FARAPULSE Endocardial Ablation System used in the subject clinical investigation consists of the FARAWAVE Endocardial Ablation Catheter System, the FARASTAR Endocardial Generator System, and the FARADRIVE Deflectable Sheath System (**Figure 1**). Model (REF#) numbers of the components used in this study are detailed in **Table 2**.

**Table 2: Components and Model Numbers of the FARAPULSE Endocardial Ablation System**

System Components	System Model Number (REF#)
FARAWAVE Endocardial Ablation Catheter System  1. Ablation Catheter (31 mm or 35 mm) 2. Extension Cable	40T401 and 40T404
FARASTAR Endocardial Generator System  1. Pulsed Electric Field Generator (PEFG) 2. Two Coaxial Cables 3. Two Pace Filter Boxes 4. Two Catheter Switch Boxes	60T401
FARADRIVE Deflectable Sheath System (or commercially available CE Marked Deflectable Sheath System such as the CE Marked Oscar Destino™ Twist UniDirectional Deflectable Guiding Sheath)*  1. Sheath 2. Dilator	20T401

CE Marked Devices That May be Used in Conjunction with FARAPULSE Endocardial Ablation System
*Oscor Destino™ Twist UniDirectional Deflectable Guiding Sheath
St. Jude BRK 98cm Transseptal Needle
MicroPace StimCor Cardiac Stimulator

**Figure 1. FARAPULSE Endocardial Ablation System Components.**  
Note: Blue dotted box shows the sterile, single-use components of the system

#### 4.4.1 FARAWAVE Endocardial Ablation Catheter System

[figure not shown]
The FARAWAVE Endocardial Ablation Catheter System consists of two (2) components: Ablation Catheter and Extension Cable, which are used together. Both components are sterile and single use only.

The ablation catheter is offered in two different sizes: 31 mm (REF 40T401) and 35mm (REF 40T404) deployed diameters, to accommodate varying pulmonary vein anatomy. Selection of either catheter will be at the investigator's discretion.

The Ablation Catheter is a multi-electrode catheter that connects electrically to the Endocardial Generator System. It consists of a multi-electrode ablation catheter with electrodes arranged on splines. The Ablation Catheter consists of a distal section with five splines that deploy into a flower-shaped configuration with five petals, a shaft section, and a proximal handle with a manually operated deployment control (Figure 2). Each petal has a single electrode that is separately wired to facilitate connection to a mapping or recording system (this is an optional feature offered to the user). The handle includes a flush port for saline infusion, a deployment control knob with a guidewire lumen hub that can be connected to a hemostasis valve, and a cable with connectors. The catheter connectors connect to an Extension cable (also part of the Endocardial Ablation

Catheter System) with numbered connectors on each of its ends. These connect to the multi-channel Endocardial Generator. The Pulsed Electric Field energy is delivered via the PEF Generator over the set of ablation catheter electrodes. The Extension Cable is a single-use sterile cable that provides additional cable length to connect to the Endocardial Generator.

Additional details are provided in the IFU LBL0195 for the specific use and procedural steps of the Endocardial Ablation Catheter System.

**Figure 2: Representative Illustration of Deployed Endocardial Ablation Catheter with Fully Deployed Distal “flower” Section.  
Provided in 31mm and 35mm Deployed Diameters**

#### **4.4.2 FARASTAR Endocardial Generator System**

The FARASTAR Endocardial Generator System consists of the following components – Pulsed Electric Field Generator (PEFG), BNC Coaxial Cable (2 units), Pace Filter Box (2 units), and Switch Box (2 units). The Endocardial Generator System is designed to deliver Pulsed Electric Field (PEF) energy to endocardial sites in the heart via the Endocardial Ablation Catheter System and other compatible devices (refer to IFU LBL0195 for the specific use and procedural steps of the Endocardial Ablation Catheter System, LBL0193 for the Deflectable Sheath System and LBL0198 for the Endocardial Generator System).

The Pulsed Electric Field Generator is a 16-channel output unit that generates a pulsed voltage waveform that can be delivered to the ablation catheter electrodes. The FARASTAR Generator, while capable of operating between 1400V and 2100V, currently allows ablation energy in discrete user-selectable voltage settings between 1400V and 2000V.

As an input, a compatible cardiac stimulator unit for cardiac pacing is applied to the cardiac chambers via pacing catheters and to the PEFG with a coaxial cable to synchronize the application of therapeutic PEF energy to the actively paced heart. The physician confirms proper synchronization by actuating a button on the

PEFG user interface. The BNC Coaxial Cable is used to connect the generator to a commercially available compatible cardiac stimulator/pacing device.

Details regarding the generator are provided in the FARASTAR Endocardial Generator System User Manual LBL0198.

#### 4.4.3 FARADRIVE Deflectable Sheath System

The FARAWAVE Endocardial Ablation Catheter is used with the FARADRIVE Deflectable Sheath System or a compatible CE Marked Deflectable Sheath System (13F) such as the CE Marked Oscar Destino™ Twist UniDirectional Deflectable Guiding Sheath.

The FARADRIVE Deflectable Sheath System consists of two (2) components: Deflectable Sheath and Dilator, which are used together. Both components are sterile and single use only (**Figure 3**).

The Deflectable Sheath is comprised of a distal deflectable section and a shaft section which connect to the handle. The handle includes a knob to control the deflection of the distal tip and a flush port for infusion of saline or contrast. The Dilator is intended for insertion through the sheath lumen and includes a shaped tip for dilation for vascular or chamber access.

**Figure 3: Deflectable Sheath and Dilator**

#### 4.5 Device Accountability

The FARAPULSE Endocardial Ablation System will be housed in a secure location and access will be controlled. Records will be maintained to document the physical location of inventory from shipment and removal from Sponsor or Contract Manufacture facility through use and / or return or disposal.

The site will be responsible for maintaining a Device Accountability Log provided by the Sponsor or its designated representative. At a minimum the following will be recorded: Date of receipt, FARAPULSE Endocardial Ablation System

identification number (lot and / or serial number), expiration date, date of use, subject unique identification code and date of disposal or return of the device.

If there is a product Device Deficiency / Malfunction or other need to return the system or system components to the Sponsor or Contract Manufacture, the Sponsor or designee should be contacted for safe product disposal and/ or return details. Appropriate CRF will be completed in the event of a Device Deficiency / Malfunction.

The Investigator is responsible for ensuring that the investigational devices are used only under the Investigator's supervision and are only used according to this protocol and any approved amendments. The Investigator will not supply an investigational device to any person not authorized to participate in the study. The Investigator shall document on the Case Report Forms (CRFs) the lot numbers and / or serial numbers of the devices used during each case.

#### **4.6 Return of Devices**

All unused investigational devices will be returned to the study Sponsor or designee upon completion of the clinical study. Any investigational device that does not meet performance specifications will also be returned to the study Sponsor or designee for analysis per company procedures. The Investigator or his/ her designated representative is responsible for device accountability and disposition of all used and unused devices. The study Sponsor or its designated representative will conduct device reconciliation at the completion of subject enrollment or at the conclusion of the study.

### **5. Study Objectives**

The objective of the safety and feasibility study is to demonstrate that the endocardial creation of electrically isolating lesions via pulsed electric field (PEF) catheter ablation applied using the FARAPULSE Endocardial Ablation System is a feasible and safe treatment for paroxysmal atrial fibrillation (PAF).

#### **5.1 Study Design**

This is a prospective, multi-center, intention-to-treat safety and feasibility study. Subjects will undergo percutaneous PEF ablation for pulmonary vein isolation. Subjects will then be followed at 7 days, 30 days, 75 days, 90 days, 6 months, and 12 months for adverse events, recurrence of arrhythmia after a 90-day blanking period and other relevant outcome measures.

#### **5.2 Selection and Withdrawal of Subjects**

##### **5.2.1 Inclusion Criteria**

Study subjects are required to meet all the following inclusion criteria to participate in this study:

1. Patients with documented drug resistant symptomatic PAF; who have:

- a. Confirmed AF: Documentation may include ECG, transtelephonic monitor (TTM), Holter monitor, implanted devices, telemetry strip or similar, recorded within one year prior to enrollment and showing at least 30 seconds of AF.
- b. Frequent AF, defined as  $\geq 2$  episodes within 6 months of enrollment.
- c. Failed AFD, meaning therapeutic failure of at least one antiarrhythmic drug (AFD; class I – IV) for efficacy and / or intolerance
2. Patients who are  $\geq 18$  and  $\leq 75$  years of age on the day of enrollment.
3. Patient participation requirements:
  - a. Lives locally
  - b. Is willing and capable of providing Informed Consent to undergo study procedures
  - c. Is willing to participate in all examinations and follow-up visits and tests associated with this clinical study.

### **5.2.2 Exclusion Criteria**

Subjects will be excluded from participating in this study if they meet any one of the following exclusion criteria:

1. Use of amiodarone within 3 months prior to enrollment
2. Atrial fibrillation that is any of the following
  - a. Persistent (by diagnosis or duration  $> 7$  days)
  - b. Secondary to electrolyte imbalance, thyroid disease, alcohol abuse or other reversible / non-cardiac causes
  - c. Requires  $\geq 3$  cardioversions in the preceding 12 months
3. Cardiac anatomical exclusions by imaging within 3 months prior to enrollment:
  - a. Left atrial anteroposterior diameter  $\geq 5.0$  cm as documented by transthoracic echocardiography (TTE) or computed tomography (CT)
  - b. Left ventricular ejection fraction  $\leq 40\%$  as documented by TTE
4. Any of the following cardiac procedures, implants or conditions:
  - a. Clinically significant arrhythmias other than AF
  - b. Hemodynamically significant valvular disease
  - c. Prosthetic heart valve
  - d. NYHA Class III or IV CHF
  - e. Previous endocardial or epicardial ablation or surgery for AF
  - f. Atrial or ventricular septal defect closure
  - g. Atrial myxoma
  - h. Left atrial appendage device or occlusion
  - i. Pacemaker, ICD or CRT
  - j. Significant or symptomatic hypotension
  - k. Bradycardia or chronotropic incompetence
  - l. History of pericarditis
  - m. History of rheumatic fever
5. Any of the following within 3 months of enrollment:
  - a. Myocardial infarction
  - b. Unstable angina

- c. Percutaneous coronary intervention
- d. Heart surgery (e.g. coronary artery bypass grafting, ventriculotomy, atriotomy)
- e. Heart failure hospitalization
- f. Stroke or TIA
- g. Clinically significant bleeding
- h. Pericarditis or pericardial effusion
- i. Left atrial thrombus

6. History of blood clotting or bleeding abnormalities.
7. Contraindication to, or unwillingness to use, systemic anticoagulation
8. Contraindications to CT or MRI
9. Sensitivity to contrast media not controlled by premedication
10. Women of childbearing potential who are pregnant, lactating or not using birth control
11. Serious or untreated medical conditions that would prevent participation in the study, interfere with assessment or therapy, or confound data or its interpretation, including but not limited to
  - a. Solid organ or hematologic transplant, or currently being evaluated for an organ transplant
  - b. Severe lung disease, pulmonary hypertension, or any lung disease involving abnormal blood gases or significant dyspnea
  - c. Chronic renal insufficiency of < 60 mL/min/1.73 m^2, any history of renal dialysis, or history of renal transplant
  - d. Active malignancy or history of treated cancer within 24 months of enrollment
  - e. Clinically significant gastrointestinal problems involving the esophagus, stomach and/or untreated acid reflux
  - f. Clinically significant infection
  - g. Predicted life expectancy less than one year
12. Clinically significant psychological condition that in the investigator's opinion would prohibit the subject's ability to meet the protocol requirements
13. Current or anticipated enrollment in any other clinical study
14. Body Mass Index (BMI) > 35
15. Distorted cardiac anatomy due to congenital heart disease

## 5.3 Study Endpoints

### 5.3.1 Primary Safety Endpoint

The primary safety endpoint for this study is the Composite Safety Endpoint (CSE) defined as the incidence of the following early-onset and late-onset serious adverse events (SAEs) which are device- or procedure-related:

Early onset (within 30 days of any endocardial ablation for atrial fibrillation)

- Death
- Myocardial infarction (MI)
- Persistent diaphragmatic paralysis
- Stroke or transient ischemic attack (TIA)
- Peripheral or organ thromboembolism
- Pericarditis
- Cardiac tamponade / perforation
- Vascular access complications
- Hospitalization (initial or prolonged)\*
- Heart block

Late onset (any time during follow-up)

- Pulmonary vein (PV) stenosis (> 70% diameter reduction from baseline)
- Atrio-esophageal fistula

\* Excludes hospitalization (initial & prolonged) solely due to arrhythmia (AF/Atrial Flutter/Atrial Tachycardia) recurrence or due to non-urgent cardioversion (pharmacological or electrical). Hospitalization excludes visits to hospital-associated outpatient facilities such as clinics or emergency wards.

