**Table 3. Primary AE Safety Endpoint Definitions**

Primary Adverse Event	Description/Criteria
Death	Death
Myocardial infarction (MI)	Myocardial infarction will be demonstrated by any one of the following: 1) detection of ECG changes indicative of new ischemia (new ST-T wave changes or new LBB) that persist for more than 1 hour. 2) development of new pathological Q waves on an ECG 3) imaging evidence of new loss of viable myocardium or new regional wall motion abnormality
Persistent diaphragmatic paralysis	Change in baseline diaphragmatic function as evidenced by elevation of the diaphragm above the normal range but not due to a pulmonary process such as atelectasis.
Stroke or transient ischemic attack (TIA)	Stroke is an acute symptomatic episode of neurological dysfunction attributed to a vascular cause (ischemia or hemorrhage) in which symptoms last more than 24 hours, or if symptoms last less than 24 hours, a brain imaging study demonstrates infarction.  Transient ischemic attack is a new focal neurological deficit with rapid symptom resolution always within 24 hours.
Peripheral or organ thromboembolism	Formation in a blood vessel of a clot (thrombus) that results from the breaking loose of all or part of an existing thrombus, which is then carried by the blood to lodge in/occlude a more distal vascular site.
Pericarditis	Inflammation of the pericardial space that results in an effusion that leads to hemodynamic compromise or required pericardiocentesis, prolongs hospitalization by more than 48 hours, requires hospitalization, or persists for more than 30 days following the ablation procedure.
Cardiac tamponade/perforation	The development of a significant pericardial effusion during or within 30 days of undergoing the index AF ablation procedure. A significant pericardial effusion is one which results in hemodynamic compromised (<80mmHg systolic bp), requires elective or urgent pericardiocentesis, or results in a 1cm or more pericardial effusion as documented by echocardiography.
Vascular access complications	Vascular access complication (e.g. groin hematoma, AV fistula, pseudoaneurysm) requiring intervention (e.g. surgical repair, blood transfusion) or admission or prolonged hospitalization.
Hospitalization (initial or prolonged)	*excludes hospitalization (initial or prolonged) solely due to arrhythmia (AF/AFL/AT) recurrence

Primary Adverse Event	Description/Criteria
	or due to non-urgent cardioversion (pharmacological or electrical)

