### 5.3.4 Secondary Feasibility Endpoint

1. The proportion of subjects that achieve Chronic Procedural Success (CPS) defined as persistent electrical isolation of all initially ablated pulmonary veins assessed during an electroanatomical mapping procedure performed 75 days following the index procedure. Chronic Procedural Success will be subdivided by single procedure and reablated subjects.
2. The proportion of subjects that achieve Therapeutic Success, defined as freedom from:
  - a. Post blanking period through assessment: occurrence of AF, AFL or AT, or ablation for AF/AFL/AT using the study device
  - b. At any time: ablation for AF/AFL/AT with a nonstudy device

Therapeutic success will be assessed from the end of the blanking period at Months 6 and 12, and will be subdivided by on / off AFDs post blanking period.

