#### **5.12.5 75 Day Follow-Up**

Subjects will return for an office visit at 75 days ( $\pm$  15 days) post index ablation. At a minimum, the following data will be collected at the 75-day follow-up visit:

- Medications including use, changes in or discontinuation of anticoagulation, rate control and/or antiarrhythmic medications
- Pregnancy test (if applicable)
- Cardiac rhythm as determined by a 12-lead ECG
- Cardiac CT or MRI scan to assess the patency of the pulmonary veins
- 3D electroanatomical remapping procedure to assess electrical isolation of the pulmonary veins. Any electrical gaps may be closed at the investigator's discretion using a commercially approved ablation device. This will consist of placement of catheters in the left atrium via femoral access and transseptal puncture using conventional electrophysiology techniques. Any electrical gaps may be closed at the investigator's discretion using the study device or, if clinically necessary, using a commercially approved ablation device (which constitutes a therapeutic treatment failure).

- An Event Monitor will be provided to be used up to the 12-month follow-up visit for weekly scheduled and ad hoc symptomatic monitoring. Subjects will retain this device through the 12-month follow-up, ECG data from this monitor will be analyzed by a contract core lab. Investigational sites will be provided with the Event Monitor device and instructions for its use by the contract core lab. The investigational sites will then provide the device and instructions for use to the subject. The Event Monitor will be returned at the end of the subject's follow-up using shipping materials provided by the core lab.
- Cardioversions since last visit
- Heart failure status as assessed by NYHA classification at the time of visit
- Fluoroscopic Examination of Diaphragm Motion if the procedural examination indicates diminished phrenic nerve response
- Anticoagulation Monitoring: For subjects on anticoagulants, assessment of INR/PTT therapeutic levels as applicable/required (maintain as clinically indicated)
- Any additional ablation procedures performed
- Any hospital readmissions, including admission and discharge dates, since the previous visit
- Adverse Events

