#### **5.12.7 6 Month Follow-up**

Subjects will return for an office visit 6 months (180 days  $\pm$  30 days) post-ablation treatment. At a minimum, the following data will be collected at 6 months:

- Medications including use, changes in or discontinuation of anticoagulation, rate control and/or antiarrhythmic medications
- Cardiac rhythm as determined by a 12-lead ECG at the time of the visit
- Cardiac rhythm as determined by a 24-hour continuous ECG monitor. ECG data from this monitor will be analyzed by a contract core lab. Investigational sites will be provided with the continuous ECG monitor device and instructions for its use by the contract core lab. The investigational sites will then provide the device and instructions for use to the subject. The device will be worn by the subject for a single 24-hour period and then returned to the core lab with shipping materials provided by the core lab.

- Event Monitor provided at the 75-day follow-up visit will be reviewed for weekly scheduled and ad hoc symptomatic monitoring. ECG data from this monitor will be analyzed by a contract core lab.
- Cardioversions since last visit
- Heart failure status as assessed by NYHA classification at the time of visit
- Fluoroscopic Examination of Diaphragm Motion if the procedural examination indicates diminished phrenic nerve response
- Anticoagulation Monitoring: For subjects on anticoagulants, assessment of INR/PTT therapeutic levels as applicable/required (maintain as clinically indicated)
- Any additional ablation procedures performed
- Any hospital readmissions, including admission and discharge dates, since the previous visit
- Adverse Events

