### *Serious Adverse Event (SAE):*

- led to death,
- led to serious deterioration in the health of the subject, that either resulted in:
  - a life-threatening illness or injury, or
  - a permanent impairment of a body structure or a body function, or
  - in-patient or prolonged hospitalization, or
  - medical or surgical intervention to prevent life-threatening illness or injury or permanent impairment to a body structure or a body function.

- led to fetal distress, fetal death or a congenital abnormality or birth defect.

NOTE: Planned hospitalization for a pre-existing condition, or a procedure required by the CIP, without serious deterioration in health, is not considered a serious adverse event.

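### A tamponade at re-ablation is inside the primary safety endpoint by section 5.3.1 but outside it by the Table 3 definition

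*Combined protocol and SAP*

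**What the plan says.** Section 5.3.1 defines the Composite Safety Endpoint as device- or procedure-related SAEs in an early-onset and a late-onset list. The early-onset list is headed "Early onset (within 30 days of any endocardial ablation for atrial fibrillation" and names cardiac tamponade / perforation. The Executive Summary and section 7.6.1 repeat this window.

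Table 3 gives the component definitions. Its tamponade/perforation row reads "The development of a significant pericardial effusion during or within 30 days of undergoing the index AF ablation procedure". It is the only row in the table tied to the index procedure.

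Several places foresee a second ablation:
- Section 5.12.5 schedules electroanatomical remapping at 75 ± 15 days after the index ablation. Gaps may be closed at the investigator's discretion "using the study device or, if clinically necessary, using a commercially approved ablation device".
- Section 5.3.4 states "Chronic Procedural Success will be subdivided by single procedure and reablated subjects".
- The data to be collected at 6 months (section 5.12.7) include "Any additional ablation procedures performed". The 12-month and unscheduled visits ask for the same.

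Section 8.1 bears on which events could enter the composite by another route. An event can be serious through "medical or surgical intervention to prevent life-threatening illness or injury or permanent impairment to a body structure or a body function" alone. The note excludes from SAEs "Planned hospitalization for a pre-existing condition, or a procedure required by the CIP, without serious deterioration in health".

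**The concern.** The list and the definition give different start points for one component of the primary safety endpoint, and nothing says which prevails. The difference matters only for ablations after the first, and the plan expects those. Two careful readers could classify the same re-ablation tamponade differently and each cite current text. If the question is first settled after such an event, the primary safety count will have been chosen with the result known.

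No test, threshold or sample size depends on the rate. However, section 7.2 justifies the 80 subjects by the event-rate estimates and confidence intervals they will give, and says the data will inform the powering of a later study. The rate should have one definition.

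**Working it through.** There is no plan figure to reproduce: section 7.1 states no formal hypothesis test and no required sample size. The check compares the wording and the dates, then sizes the effect.

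**1. Wording side by side**

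| Place | Window for tamponade/perforation |
|---|---|
| Executive Summary | 30 days from *any* endocardial AF ablation |
| Section 5.3.1 | 30 days from *any* endocardial AF ablation |
| Section 7.6.1 | 30 days from *any* endocardial AF ablation |
| Table 3 | during or within 30 days of the *index* ablation |

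*Index* cannot be read as *any*. The Executive Summary runs the 90-day blanking period from the initial procedure, and section 5.6 runs the same period from the index procedure. Section 5.3.4 separates single-procedure from reablated subjects.

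**2. Timing** (section 5.12.5, Table 4)

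- Remap window: 75 − 15 = day 60 to 75 + 15 = day 90.
- The Table 3 window closes at day 30, so the gap is at least 60 − 30 = 30 days.

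A re-ablation at an in-window remap, or at any later visit, is always outside the Table 3 window. Only an effusion after a repeat ablation that still falls within 30 days of the index procedure meets both wordings.

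**3. Which events change class**

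The tamponade component differs for every re-ablation tamponade that is a related SAE. The composite differs only if no other component captures the event.
- *Hospitalization* captures it if the stay is prolonged or a new admission follows. Under section 8.1 a planned admission for a procedure the plan requires is not itself an SAE, whereas intervention alone can make an event serious.
- *Pericarditis* requires inflammation of the pericardial space. A perforation effusion need not meet that.

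The case that changes class is therefore a re-ablation tamponade drained without a longer stay and not captured by another component.

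**4. Size per subject**

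Shift = 100/N percentage points: 100/80 = 1.25. Enrolment is up to 80 and section 7.4 uses available data only, so N may be smaller. For illustration, 100/60 = 1.67 and 100/40 = 2.50.

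Exact (Clopper-Pearson) 95% limits are the 0.025 quantile of Beta(x, n − x + 1) and the 0.975 quantile of Beta(x + 1, n − x). With n = 80:

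| Subjects with event | Rate | 95% CI |
|---|---|---|
| 0 | 0% | 0 to 4.5% |
| 1 | 1.25% | 0.03 to 6.8% |
| 2 | 2.50% | 0.30 to 8.7% |

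**5. How often the setting could arise**

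In IMPULSE (section 3.4.1, same system), 24 patients were remapped and 8 had all veins isolated. So 24 − 8 = 16 had a reconnected vein: 16/24 = 66.7% (exact 95% CI 44.7 to 84.4%). If that share applied and all 80 were remapped, 80 × 0.667 = 53 subjects (36 to 67) would be candidates for closure. This counts candidates; it does not count re-ablations, tamponades or reclassified subjects.

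**The case against.** The strongest reply is that this is a drafting slip with little consequence. Three of the four statements agree, including the operative definition and the analysis section, and *index* appears in only one row of Table 3. To change the composite, an event needs a gap, a discretionary closure, a tamponade, serious and related status, and no capture by Hospitalization or another component. An inflammatory effusion needing drainage could still count under Pericarditis, which Table 3 does not tie to the index procedure. Secondary safety endpoint 1 captures every device- or procedure-related SAE in any case, the Clinical Events Committee adjudicates, and no decision threshold depends on the composite.

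Most of this stands. The affected case is narrow, the documents give no frequency for it, and no event disappears from the safety data. The figure of 53 candidates is context only.

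It does not remove the contradiction. Section 10.10 asks the committee to classify events but gives no rule of precedence between the list and Table 3. A haemorrhagic perforation need not meet the Pericarditis definition. A likely slip in a primary endpoint definition still has to be corrected, preferably before an event depends on it.

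**Conclusion.** The concern holds. The tamponade/perforation row of Table 3 contradicts sections 5.3.1 and 7.6.1 and the Executive Summary, and as written it would drop a re-ablation tamponade that the endpoint definition counts. The passages must be reconciled.

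The effect is bounded. Power and sample size are untouched. Each reclassified subject moves the composite by 1.25 points at 80 analysed, and by more if fewer are analysed. The number reclassified may be zero, because closure is discretionary and Hospitalization will capture some events under either wording. The 53-of-80 figure assumes that the IMPULSE share carries over and that all 80 are remapped. Confidence in the inconsistency is high; how often it will matter cannot be determined from the documents.

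**What to change.** In the tamponade/perforation row of Table 3, replace the index-procedure anchor with any endocardial ablation for atrial fibrillation, to match the three concordant statements. Leave the other rows as they are.

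Count each subject once in the composite, since a re-ablated subject has more than one window. Add one descriptive table of composite events by index procedure, re-ablation with the study device and re-ablation with a commercial device, so that both the index-only and the all-procedure rates can be read.

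One further suggestion is advisory. Remapping itself involves left atrial access: "This will consist of placement of catheters in the left atrium via femoral access and transseptal puncture using conventional electrophysiology techniques". A remap without ablation opens no early-onset window in any section. That wording is consistent and so is a design choice, and secondary safety endpoint 1 covers the related SAEs. Showing these in a remap-only row beside the composite, not inside it, would be informative.

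The cost is one phrase and one table. The visit schedule already collects adverse events and additional ablations to 12 months, and the Clinical Events Committee already adjudicates procedure-related events. Section 8.2 describes adverse-event monitoring as ending at discharge; it should be clarified to agree with the visit schedule, because re-ablation events come later. The one drawback for the sponsor is that the all-procedure rate may look slightly less favourable than the index-only rate.
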